- **Treatment Period 1 (subjects who receive an IV loading dose of investigational product and who participate in Treatment Period 2):** From the date / time of the first SC administration of investigational product in Treatment Period 1 (ie, at the Week 1 [Day 6] Visit) until the date / time of the first administration of investigational product in Treatment Period 2 (ie, at the Week 13 [Day 91] Visit).
- **Treatment Period 1 (subjects who receive an IV loading dose of investigational product and who do NOT participate in Treatment Period 2):** From the date / time of the first SC administration of investigational product in Treatment Period 1 (ie, at the Week 1 [Day 6] Visit) until the Week 13 (Day 91) Visit date and time.
- **Treatment Period 1 (CCI [REDACTED]):** From the date / time of the second SC administration of investigational product in Treatment Period 1 (ie, at the Week 3 [Day 15] Visit) until the date / time of the first administration of investigational product in Treatment Period 2 (ie, at the Week 13 [Day 85] Visit).
- **Treatment Period 1 (CCI [REDACTED]):** From the date / time of the second SC administration of investigational product in Treatment Period 1 (ie, at the Week 3 [Day 15] Visit) until the Week 13 (Day 85) Visit date and time.
- **Treatment Period 2 (subjects assigned to CCI mg):** From the date / time of the third administration of investigational product in Treatment Period 2 (ie, at the Week 21 [Day 147] Visit) until the Week 57 (Day 399) Visit date and time.
- **Treatment Period 2 (subjects assigned to CCI mg):**
 - From the date / time of the third administration of investigational product in Treatment Period 2 (ie, at the Week 21 [Day 147] Visit) until the Week 57 (Day 399) Visit date and time OR time point of planned switch to CCI mg (per protocol Amendment 2), whatever occurs first OR
 - From the date / time of planned switch to CCI mg (per protocol Amendment 2) until the Week 57 (Day 399) Visit date and time.

The evaluation period for assessment of efficacy in Treatment Period 2 will be extended to the subject's final Treatment Period 2 visit for subjects who are in the Extended Treatment Period 2.

Hereditary angioedema attacks with a start date between the first and second administrations of the investigational product in Treatment Period 1 will not be included in the analyses of efficacy, but will be presented in a listing (only).

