## 5 Changes in the Conduct of Planned Analyses

Changes after finalization of this SAP will either be described in a protocol amendment or in an update to the SAP. They will be clearly indicated in the CSR.

Changes in the analysis following Amendment 2 are as follows:

Efficacy analysis: the planned treatment for the efficacy analysis is the randomized treatment. Following Amendment 2, for subjects randomized to [REDACTED] mg CSL312 q4wk in Treatment Period 2 their planned treatment will be reduced to [REDACTED] mg CSL312 q4wk. The subjects will be reported under this treatment after the planned dose reduction. For subjects who receive continuously the same dose of CSL312 during both treatment periods, data will be included in the analysis until the planned dose reduction following Amendment 2.

Safety analysis: the actual treatment will be used for the Safety analysis. Subjects with planned or unplanned dose reduction or allowed dose increase will be reported under the treatment they actually received. For subjects who receive continuously the same dose of CSL312 during both treatment periods, data will be included in the analysis until any dose change.

The second and third interim analysis will be combined into one.

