The data from Treatment Period 1 and Treatment Period 2 will be analyzed separately. For subjects who received continuously the same dose of CSL312 during both treatment periods, the two treatment periods will also be analyzed together. For C1-INH subjects having a dose change in Treatment Period 2, only data until the date and time of the dose change will be included in these summaries over both treatment periods for the safety analyses. For efficacy analyses, data until the date and time of the planned dose reduction will be included in these summaries over both treatment periods.

In Treatment Period 1, subjects with C1-INH HAE who are treated with placebo, [REDACTED] mg, [REDACTED] mg, or [REDACTED] mg CSL312 q4wk will be analyzed separately from subjects with C1-INH HAE who are treated with [REDACTED] mg CSL312 q2wk. In both treatment periods, subjects with FXII/PLG HAE will be analyzed separately from subjects with C1-INH HAE.

Summaries will be reported by treatment period and treatment in the following order:

- Treatment Period 1 FXII/PLG HAE: [REDACTED] mg CSL312 q4wk;
- Treatment Period 2 FXII/PLG HAE: [REDACTED] mg CSL312 q4wk;
- Treatment Period 1 & 2 FXII/PLG HAE: [REDACTED] mg CSL312 q4wk;
- Treatment Period 1 C1-INH HAE: placebo, [REDACTED] mg, [REDACTED] mg, and [REDACTED] mg CSL312 q4wk, Total Blinded Part and Total CSL312 (no totals will be populated for efficacy; for PK, [REDACTED] only Total CSL312);
- Treatment Period 1 C1-INH HAE: [REDACTED] mg CSL312 q2wk;
- Treatment Period 2 C1-INH HAE: [REDACTED] mg (initial and after down-titration), [REDACTED] mg in the Safety analysis], [REDACTED] mg CSL312 q4wk, and Total (no total will be populated for efficacy);
- Treatment Period 1 & 2 C1-INH HAE: [REDACTED] mg, [REDACTED] mg CSL312 q4wk, and Total (no total will be populated for efficacy) – only data included until dose change (Safety analysis) or planned dose reduction (Efficacy analysis).

The by-subject listings will include treatment period, treatment, subject number, and basic demographics (sex, age, body mass index [BMI]), and the information specific to that listing. The laboratory normal reference ranges will be provided and clinical laboratory test results outside the normal reference range will be flagged in the laboratory data listings.

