### 7.2 Treatment Descriptors

C1-INH HAE: Treatment Period 1 Blinded			
Placebo q4wk	●●● mg CSL312 q4wk	●●● mg CSL312 q4wk	●●● mg CSL312 q4wk

C1-INH HAE Treatment Period 1 Open-label
●●● mg CSL312 q2wk

C1-INH HAE: Treatment Period 2 Open-label		
CCI mg CSL312 q4wk	CCI mg CSL312 q4wk	CCI mg CSL312 q4wk

**CCI** mg CSL312 will be included only for the Safety analysis; **CCI** mg will include planned (for Efficacy and Safety analysis) and unplanned dose reduction for Safety analysis.

FXII/PLG HAE: Treatment Period 2 Open-label
CCI mg CSL312 q4wk

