**Treatment Period 1 (CCI [REDACTED]):** From Week 3 Day 15 Visit of Treatment Period 1 (the date / time of the second SC administration of investigational product in Treatment Period 1) until the date / time of the Week 13 Day 85 Visit (the date / time of the first administration of investigational product in Treatment Period 2) or the Study Completion Visit date and time (whichever occurs earlier). The duration (days) of the efficacy evaluation period for Treatment Period 1 will be: Week 13 Day 85 Visit date and time or Study Completion Visit date and time – Week 3 Day 15 Visit date and time + 1.

**Treatment Period 2 (subjects assigned to [REDACTED] mg CSL312 and FXII/PLG HAE subjects):** Treatment Period 2 will start after it is assumed that all subjects have achieved steady-state under CSL312. From Week 21 Day 147 Visit of Treatment Period 2 (the date / time of the third administration of investigational product in Treatment Period 2) until the date / time of the Study Completion Visit. The duration (days) of the efficacy evaluation period for Treatment Period 2 will be:

Study Completion Visit date and time – Week 21 Day 147 Visit date and time + 1.

**Treatment Period 2 (C1-INH HAE subjects assigned to [REDACTED] mg CSL312):** Treatment Period 2 will start after it is assumed that all subjects have achieved steady-state under CSL312.

- [REDACTED] mg portion: From Week 21 Day 147 Visit of Treatment Period 2 (the date / time of the third administration of investigational product in Treatment Period 2) until the

date / time of the Study Completion Visit OR the date / time of the planned dose reduction to [REDACTED] mg (following Amendment 2), whatever occurs first. The duration (days) of the efficacy evaluation period for [REDACTED] mg in Treatment Period 2 will be:  
(Study Completion Visit date and time or Date and time of planned dose reduction, whichever occurs first) – Week 21 Day 147 Visit date and time + 1;

- **[REDACTED] mg portion:** From the date / time of the planned dose reduction to [REDACTED] mg (following Amendment 2) until the Study Completion Visit date / time. The duration (days) of the efficacy evaluation period for [REDACTED] mg in Treatment Period 2 will be: Study Completion Visit date and time – Date and time of planned dose reduction.

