## 10 Efficacy

The primary efficacy endpoint will be summarized for the ITT and PP populations. CCI

Tables will be presented by treatment as described in Section 7.2 and treatment period. The planned treatment will be used. This is the randomized treatment before planned dose reduction following Amendment 2. After planned dose reduction following Amendment 2, the planned treatment is the reduced dose (CCI mg) for the C1-INH HAE subjects randomized to CCI mg in Treatment Period 2. Unplanned dose reductions or dose increase to CCI mg CSL312 q4wk will not be considered for the Efficacy analysis.

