### 10.1.2 Supporting Analysis: Time-normalized Number of HAE Attacks in Treatment Period 1 and 2 (Open-label Part)

In addition to the primary analysis, the time-normalized number of HAE attacks per month will also be summarized descriptively for the [REDACTED] mg and [REDACTED] mg CSL312 q4wk regimens for the following:

- Treatment Period 2 evaluation period (alone).
- Treatment Period 1 and Treatment Period 2 evaluation periods (combined) for subjects who received the same dose continuously during both treatment periods (data will only be included until the date of the planned dose reduction following Amendment 2 in Treatment Period 2).

The time-normalized number of HAE attacks per month will also be summarized descriptively for the [REDACTED] mg CSL312 q2wk regimen for subjects with C1-INH HAE for the efficacy evaluation period of Treatment Period 1 and for the [REDACTED] mg CSL312 q4wk regimen for subjects with FXII/PLG HAE for the efficacy evaluation periods of Treatment Period 1, Treatment

Period 2, and combined Treatment Period 1 and Treatment Period 2 (only applicable for subjects with FXII/PLG HAE).

The efficacy evaluation periods are defined in Section 8.2.8.

There will be no testing of the of [CCI] mg CSL312 q2wk dose against placebo q4wk or the [CCI] mg CSL312 q4wk dose against placebo q4wk for subjects with FXII/PLG HAE.

Subjects profiles will be generated for each subject. Subjects will be grouped by treatment sequence as for the by-subject listings as described in Section 7. The x-axis will show the Run-in Period, Treatment Period 1 and Treatment Period 2. The different subject IDs will be plotted on the y-axis. [CCI]

[REDACTED]

[REDACTED]

[REDACTED]

[REDACTED]

[REDACTED]

Subject profiles will be reviewed to detect possible patterns of missing values due to drop-outs, e.g., due to many attacks.

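### In the descriptive Treatment Period 2 efficacy summaries, the reduced-dose window has no steady-state lead-in and is pooled with subjects who began on the lower dose

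*SAP*

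**What the plan says.** SAP 8.2.8 gives its reason for the late start: "Treatment Period 2 will start after it is assumed that all subjects have achieved steady-state under CSL312". The Treatment Period 2 window for subjects on their assigned dose therefore opens at the Week 21 (Day 147) visit, the third administration of that period. For C1-INH HAE subjects assigned to the higher dose, the same section splits the period. The higher-dose portion also opens at Day 147 and ends at the planned reduction. The lower-dose portion is defined as running "From the date / time of the planned dose reduction to" the lower dose (figure redacted) until study completion. Protocol 10.3 has the same rule: "From the date / time of planned switch to".

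Four places in the SAP assign these data to the lower dose:

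- Section 5: "The subjects will be reported under this treatment after the planned dose reduction".
- Section 7, in the list of reporting columns: "mg (initial and after down-titration".
- Section 7.2, on the lower-dose column: "mg will include planned (for Efficacy and Safety analysis) and unplanned dose reduction for Safety analysis".
- Section 10: "After planned dose reduction following Amendment 2, the planned treatment is the reduced dose".

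The summary most directly concerned is the descriptive attack rate in SAP 10.1.2 for the "Treatment Period 2 evaluation period (alone"). The secondary attack summaries in SAP 10.2 use the same windows.

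**The concern.** The SAP applies its steady-state principle to one part of the lower-dose column and not to the other. Subjects who start Treatment Period 2 on the lower dose contribute nothing until their third administration. Subjects who are reduced contribute from the moment of reduction, while drug from the higher dose is still circulating. If higher exposure prevents more attacks, the lower dose gets credit for protection that the higher dose provided. Protocol 3.3.1 says that the study's data will inform dose selection for a possible phase 3 study, so a dose-specific attack rate should describe that dose as far as possible.

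A related wording problem sits in the same section. SAP 8.2.8 lists attacks starting between Day 85/91 and Day 147 among those shown in listings only. The sentence that introduces the list, and SAP 10.1, exclude only attacks outside the defined windows. Two windows can contain those days: the combined Treatment Period 1 and 2 window, and a reduced-dose window that opens before Day 147. In both it is unclear whether attacks are dropped while their days stay in the denominator.

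**Working it through.** **Inputs.** Half-life about 19 days with linear kinetics (Protocol 1.2.3.1); 28-day dosing (Protocol 3.2.2); reduction at the next scheduled visit (Protocol 5.5); visits at Days 147, 231, 315 and 399 (Protocol 8.5.4). The dose ratio r is redacted in the running text, so r = 2 and r = 3 are assumptions.

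**The plan's own lead-in.** First Treatment Period 2 dose at Day 91, so the third falls at 91 + 2 × 28 = Day 147, which reproduces the SAP. The lead-in is 147 − 91 = 56 days, or 56/19 = 2.9 half-lives (62 days for subjects coming from q2wk dosing, who start at Day 85). After the reduction it is 0 days.

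**Persisting excess.** The visits from Day 147 on are 84 days = 3 dosing intervals apart, so a switch at one of them falls at trough. With k = ln 2/19 = 0.0365 per day, τ = 28, instant absorption and higher-dose steady state at the switch:

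- trough/average = kτ·e^(−kτ)/(1 − e^(−kτ)) = 0.575
- mean persisting share over days a to b: f(a,b) = 0.575·(e^(−ka) − e^(−kb))/(k(b − a))
- f(0,28) = 0.360; f(28,56) = 0.130; f(56,84) = 0.047

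**Mean exposure relative to lower-dose steady state.** Over a reduced-dose window of W days it is 1 + (r − 1)·f(0,W). For the pooled column, at most about 20 subjects start Treatment Period 2 on each dose (8 continuing plus half of up to 24 re-randomized), and rates are calculated per subject. Reduced subjects can therefore be up to about half of the column, which gives 1 + (r − 1)·f(0,W)/2 if the initial subjects are taken as 1.00.

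| Window W | Reduced subjects, r = 2 / 3 | Pooled column, r = 2 / 3 |
|---|---|---|
| 84 days (reduction Day 315, completion Day 399) | 1.179 / 1.358 | 1.089 / 1.179 |
| 168 days (Day 231) | 1.094 / 1.187 | 1.047 / 1.094 |
| 252 days (Day 147) | 1.063 / 1.125 | 1.031 / 1.063 |
| 336 days (with extension) | 1.047 / 1.094 | 1.023 / 1.047 |

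**Sensitivity to absorption.** An assumed SC absorption half-life of 1 to 5 days gives, for reduced subjects, 1.19–1.24 (r = 2) and 1.38–1.48 (r = 3) at 84 days, and 1.07–1.08 and 1.13–1.17 at 252 days. The slowest 84-day case, pooled, is 1 + 0.24/2 = 1.12 and 1 + 0.48/2 = 1.24.

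**With the SAP's own 56-day lead-in after the reduction**, reduced-subject exposure falls to 1.047 / 1.093 (84-day window), 1.018 / 1.036 (168) and 1.010 / 1.021 (252).

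**Early reductions.** By the SAP formula the higher-dose portion lasts 147 − 147 + 1 = 1 day for a reduction at Day 147, and 119 − 147 + 1 = −27 days for one at Day 119.

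**Combined window.** For a subject on one dose from Day 6 to Day 399, Days 91 to 147 are 56 of 399 − 6 + 1 = 394 days (14%). A literal reading of the list would drop attacks in that stretch and keep the days.

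**The case against.** The rule is deliberate and consistent. Both documents define the ITT population by assigned treatment and expressly include the reduced dose after the reduction (Protocol 10.2.2, SAP 6.2). Efficacy follows assignment, so dose increases and unplanned reductions are ignored too (SAP 10). Counting from the assignment date is a legitimate convention. This stands as a defence of the label, but it does not explain why one part of the column has a lead-in on stated steady-state grounds and the other has none.

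The comparisons that matter most are protected. The Treatment Period 2 responder comparison between doses uses only pre-reduction data (SAP 10.2.1), and the combined-period summary stops at the planned reduction (SAP 8.2.8). Treatment Period 1 holds the placebo tests and the direct dose-against-dose test. A reader might infer that the efficacy conclusions or the primary tests are biased; the documents do not support that, because no post-reduction data enter them. Nor does Protocol 3.3.1 give this particular column a role in dose selection.

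The two groups are not hidden. Listings are sorted by treatment sequence and report dose changes (SAP 7), derived rates are listed by subject (SAP 10.1), and subject profiles span all periods (SAP 10.1.2). It also cannot be claimed that no sensitivity summary exists: SAP 10.1.3 to 10.1.5 are redacted. What can be said is that no visible summary separates the groups.

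On early reductions, no document shows that one occurred before Day 147. The introductory sentence in SAP 8.2.8 and SAP 10.1 suggest that the window governs, in which case the negative duration simply means an empty window. That is probably the intent, but the list contradicts it.

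**Conclusion.** The point holds as a modest inconsistency in descriptive, open-label summaries. The Treatment Period 2 attack summaries for the lower dose contain some higher-dose exposure. Under instant absorption, a switch at trough and an equal split of subjects, the pooled excess is about 2–9% for an assumed dose ratio of 2 and 5–18% for a ratio of 3. It is larger for late reductions and for slower absorption.

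These are exposure ratios. A reader might turn them into an overstatement of the lower dose's efficacy; the documents do not allow that. Protocol 3.3.2 says the inhibition level needed to prevent attacks is unknown, and neither the dose ratio nor the switch dates are available. The direction is known only if the two doses differ in attack prevention, and the effect may be small.

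Carry-over does not affect the Treatment Period 1 tests, the Treatment Period 2 responder comparison or the combined-period summary. It does reach the Treatment Period 2 safety tables: SAP 8.2.7 reports subjects under the modified dose from the dose change, and the post-change exposure and adverse-event windows in SAP 8.2.8 open there as well, again without a lead-in. Priority lies between optional and a low-level recommendation; the low cost is the main reason to act.

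**What to change.** 1. In SAP 7, 7.2 and 10.1.2, show *initial* and *after planned reduction* data in separate Treatment Period 2 efficacy columns. This adds one column and loses no data.
2. Add a sensitivity summary in which the post-reduction window starts at the third reduced-dose administration, with both the attacks and the days before it removed. It costs 56 days of follow-up per affected subject, leaving 28, 112 or 196 days of an 84-, 168- or 252-day window. It is imprecise for late reductions, so it should accompany the main summary and not replace it.
3. In SAP 8.2.8, limit the listed-only rule for Day 85/91 to Day 147 to the windows for Treatment Period 2 alone. State for every window, including the combined one and any reduced-dose window that opens before Day 147, that an attack is counted if and only if its day is in the denominator. State also that the higher-dose portion is not evaluable when the reduction is at or before Day 147.

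The total cost is wording in four SAP sections, one table column and one sensitivity table. No dose or clinical rule changes.

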### 8.2.8 Study Periods Relative to Treatment

The following definitions for the evaluation periods of efficacy and safety will be used to define the durations used in the denominator of the time-normalized endpoints and safety endpoints such as exposure and subject-years. It is not intended to re-assign assessments made during scheduled visits based on these definitions. Scheduled visits will not be re-labelled based on subject's study days irrespective of whether the visit takes place in the planned time window.

The Study Completion Date Visit in this study is at the end of Treatment Period 1 or Treatment Period 2 or at the time of premature study discontinuation. This visit is followed by the Follow-up Visit which may be waived in place of a telephone contact.

**Efficacy Analysis:** The evaluation periods will be:

**Run-in Period (all subjects):** From Week 1 Day 1 of the Run-in Period until the date / time of the Week 1 Day 1 Visit of Treatment Period 1 (the date / time of the first administration of

investigational product in Treatment Period 1) or the Study Completion Visit date and time (whichever occurs earlier). The duration (days) of the Run-in period will be:

Week 1 Day 1 Visit date and time of Treatment Period 1 or Study Completion Visit date and time – Week 1 Day 1 Visit date and time of Run-in + 1.

**Treatment Period 1 (subjects who receive an IV loading dose of investigational product):** From Week 1 Day 6 Visit of Treatment Period 1 (the date / time of the first SC administration of investigational product in Treatment Period 1) until the date / time of the Week 13 Day 91 Visit (the date / time of the first administration of investigational product in Treatment Period 2) or the Study Completion Visit date and time (whichever occurs earlier). The duration (days) of the efficacy evaluation period for Treatment Period 1 will be: Week 13 Day 91 Visit date and time or Study Completion Visit date and time – Week 1 Day 6 Visit date and time + 1.

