**Treatment Period 1 and 2 (subjects who receive an IV loading dose of investigational product and who participate in Treatment Period 2):** From Week 1 Day 6 Visit of Treatment Period 1 (the date / time of the first SC administration of investigational product in Treatment Period 1) until the date / time of the Study Completion Visit or the date / time of planned dose reduction, whichever occurs first. The duration (days) of the efficacy evaluation period for Treatment Period 1 and 2 will be:

Study Completion Visit date and time or Date and time of planned dose reduction, whichever occurs first – Week 1 Day 6 Visit date and time + 1.

After planned dose reduction, data will not be included in the summary tables.

HAE attacks with start dates outside the above specified efficacy evaluation periods will not be included in the efficacy analysis but will only be listed:

- HAE attacks with a start date between the first and second administrations of the investigational product in Treatment Period 1,
- HAE attacks with a start date between Week 13 Day 85/91 and Week 21 Day 147,
- HAE attacks with start date between date of last treatment period visit and Follow-up.

**Safety Analysis Exposure:** The duration in days of the evaluation periods will be:

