## 10.1 Primary Efficacy: Analysis of Time-Normalized Number of HAE Attacks in Treatment Period 1 (Blinded Part)

The ITT population will be used for the primary analysis and the PP will be used as the secondary.

As outlined in Section 8.2.8, HAE attacks with a start date not falling into the efficacy evaluation period will not be included in the analyses of efficacy but will be presented in a listing only.

Subjects will enter HAE symptoms into their eDiary and the start and end date and time, the interference of HAE symptom(s) with daily activities, and location(s) of the HAE symptom(s). Investigator-reported HAE attacks will be based upon review of subject diaries, relevant interval medical history, and physician judgment. The investigator may ask clarifying questions to assist in his/her assessment of whether or not an HAE attack occurred. If an attack occurred, then the investigator will record an attack in the eCRF, the start/end date, the attack location(s), and the severity of the attack based on the most severe symptoms. For every visit, the Investigator will report all HAE attacks that have occurred in the interim since the last visit the subject attended.

For the analyses, a HAE attack is defined based on the HAE attacks reported by the investigator using the HAE attack eCRF.

In the primary analysis, only subjects with C1-INH HAE who receive q4wk SC dosing (after an IV loading dose) in a blinded manner will be included. The evaluation periods are defined in Section 8.2.8.

The time-normalized number of HAE attacks per month during Treatment Period 1 for a subject will be calculated as:

$$(\text{number of HAE attacks} / \text{length of subject's evaluation period in days}) * 30.4375$$

where the length of subject's evaluation period is defined in Section 8.2.8.

The time-normalized number of HAE attacks per month will be summarized descriptively including median (primary) and mean (secondary) with corresponding 95% CIs by blinded treatment (i.e., placebo, or bci mg, bci mg, or bci mg CSL312 q4wk).

To test for a difference in the primary efficacy endpoint between [b] mg CSL312 q4wk or [b] mg CSL312 q4wk and placebo q4wk, pairwise comparisons will be performed by testing the hypotheses using a two-sided Mann-Whitney test.

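### SAP 8.2.8 does not settle whether attacks starting on Days 91–147 count in the combined Treatment Period 1 and 2 analysis; dropping them would understate a constant rate by 14.2% at Day 399

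*SAP*

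**What the plan says.** SAP 8.2.8 states that its evaluation periods "will be used to define the durations used in the denominator of the time-normalized endpoints". For subjects with an IV loading dose it sets three windows that matter here:

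- Treatment Period 1: Day 6 to Day 91.
- Treatment Period 2: Day 147 onward, on the assumption that steady state has been reached by then.
- Treatment Periods 1 and 2 combined: Day 6 to the Study Completion Visit or the planned dose reduction. The duration formula ends "whichever occurs first – Week 1 Day 6 Visit date and time + 1", and nothing is deducted for Days 91–147.

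The exclusion rule follows: "HAE attacks with start dates outside the above specified efficacy evaluation periods will not be included in the efficacy analysis". Three listing-only categories stand under it:

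1. "HAE attacks with a start date between the first and second administrations of the investigational product in Treatment Period 1"
2. "HAE attacks with a start date between Week 13 Day 85/91 and Week 21 Day 147"
3. "HAE attacks with start date between date of last treatment period visit and Follow-up"

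The combined analysis is required by SAP 7 ("For subjects who received continuously the same dose of CSL312 during both treatment periods, the two treatment periods will also be analyzed together") and again in SAP 10.1 (derived-variable listing), 10.1.2 and 10.2. SAP 10.1 repeats the window rule: "HAE attacks with a start date not falling into the efficacy evaluation period will not be included in the analyses of efficacy". Protocol 10.3.2.1.2 names a combined summary. Protocol 10.3 gives no separate combined window, and the only attacks it expressly makes listing-only are those between the first and second administrations.

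**The concern.** The first and third categories lie outside the combined window, so they agree with the lead-in. The second lies inside it. It makes sense for the separate-period analyses, where Days 91–147 belong to neither denominator, but nothing limits it to them.

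Two programmers following the SAP could therefore report different combined rates. One would apply the bullet as a global exclusion flag and take the denominator from the formula. The other would count every attack inside the window. Under the first approach attacks are lost while their days are kept, so the error can only favour CSL312.

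The outputs exposed are the combined attack rate, responder status, treated-attack rate and attack-free count (C1-INH and FXII/PLG HAE), and the on-demand use rate for C1-INH HAE only (SAP 10.3.2).

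**Working it through.** The documents give no figure for this effect, so there is nothing to reproduce. Every figure below assumes the bullet is applied to the combined analysis; under the lead-in reading each effect is zero.

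**Inputs.** Combined start Day 6, gap Day 91 to Day 147, and duration = end − start + 1 (SAP 8.2.8). Unextended end Day 399 (Protocol 10.3). Month = 30.4375 days (SAP 8.2.3). Planning rates 2.9 (placebo) and 0.6 (CSL312) attacks per month (SAP 4.5).

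**Understatement at a constant attack rate** = dropped days / denominator days, with dropped days = 147 − 91 = 56 and denominator = end day − 6 + 1.

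| End of combined window | Denominator (days) | Understatement |
|---|---|---|
| Day 231 (illustrative planned reduction) | 226 | 56/226 = 24.8% |
| Day 315 (illustrative planned reduction) | 310 | 56/310 = 18.1% |
| Day 399 (not extended) | 394 | 56/394 = 14.2% |
| Day 483 (illustrative extension) | 478 | 56/478 = 11.7% |
| Day 567 (illustrative extension) | 562 | 56/562 = 10.0% |

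The first two rows can apply only to the one continuing C1-INH arm with a planned reduction (8 planned subjects). Counting 55 or 57 dropped days moves the Day 399 figure to 14.0% or 14.5%.

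**At 0.6 attacks per month to Day 399:**
- Expected attacks: 0.6 × 394 / 30.4375 = 7.77.
- Expected attacks dropped: 0.6 × 56 / 30.4375 = 1.10.
- Probability that at least one is dropped (Poisson): 1 − exp(−1.104) = 0.67.
- Expected reported rate: 0.6 × 338 / 394 = 0.515.

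**One subject with 8 attacks.** The understatement is that subject's share of attacks starting in the gap, Binomial(8, 56/394): 0% with probability 0.29, 12.5% with 0.39, and 25% or more with 0.32.

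**Responder status.** The plan gives no Run-in rate; I assume 2.9 per month, fixed, borrowed from the placebo assumption. A responder then has at most 1.45 × 394 / 30.4375 = 18.8, that is 18, counted attacks. The Poisson mean is rate × 394 / 30.4375 with all attacks counted and rate × 338 / 30.4375 with the gap attacks dropped.

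| True rate per month | Reduction | P(responder), all counted | P(responder), gap dropped |
|---|---|---|---|
| 0.6 | 79% | 0.9995 | 0.9999 |
| 1.16 | 60% | 0.818 | 0.935 |
| 1.595 | 45% | 0.329 | 0.589 |

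**Attack-free proportion** = exp(−rate × days / 30.4375), with 394 days (correct) or 338 days (gap dropped).

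| Rate per month | 394 days | 338 days | Difference (points) |
|---|---|---|---|
| 0.05 (assumed) | 52.3% | 57.4% | 5.0 |
| 0.1 (assumed) | 27.4% | 32.9% | 5.5 |
| 0.2 (assumed) | 7.5% | 10.9% | 3.3 |
| 0.6 (plan) | 0.04% | 0.13% | 0.1 |

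Differences are taken before rounding.

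**Subjects exposed:** two continuing C1-INH arms of 8 plus up to 10 FXII/PLG subjects, 8 + 8 + 10 = 26 at most.

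**The case against.** The strongest reply is that the SAP already supplies the rule. The bullets follow a lead-in about attacks outside the periods specified above it, and the combined window is one of those periods. SAP 10.1 repeats the window test rather than the bullet. The reference to Day 85 points the same way: that day belongs to the q2wk arm, which has no combined window, so the bullet was evidently written for the gap before Treatment Period 2 efficacy begins. Dataset specifications in a separate document (SAP 8.2) may also settle the matter. This reading is plausible, and it gives zero bias. It does not remove the conflict, because the bullet is explicit, is not limited in scope, and names days that the combined denominator keeps.

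The sizes also need care. For a subject who completes without a planned reduction, 14.2% is the largest expected value, since extension lowers it. The 45% responder example is near the worst case: in that model the shift peaks there at 26 points, and it is 11.6 points at a 60% reduction and 0.04 at the planned 0.6 per month. The attack-free examples at 0.05 and 0.1 lie on either side of the maximum, about 5.6 points near 0.08. These are upper illustrations, not expectations.

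Finally, combining the two evaluation periods could mean their union, with Days 91–147 left out of both numerator and denominator. That would be coherent, but it is not the duration formula the SAP gives.

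**Conclusion.** The inconsistency is real and should be fixed before the combined outputs are programmed. The documents do not show which reading will be implemented. If the bullet is applied, the expected understatement of a constant attack rate is 14.2% for an end at Day 399, smaller with extension, and larger for C1-INH subjects whose window ends earlier at a planned reduction. If the lead-in governs, it is zero.

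With the plan's 0.6 attacks per month, and the Run-in rate assumed at 2.9, the effect on responder and attack-free proportions is about 0.1 percentage point or less; larger effects need the assumed rates shown above. The combined summaries are descriptive and have no placebo column, and the primary comparison (Day 6 to Day 91) is untouched. The point merits correction because the possible error runs in one direction only and costs almost nothing to remove.

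**What to change.** In SAP 8.2.8, state that the Day 85/91 to Day 147 listing-only category applies to the separate-period analyses only, and that numerator and denominator must cover the same days in every analysis. For the combined analysis, count attacks starting on Days 91–147 over the continuous period already defined. Since that analysis includes only subjects who stay on the same dose, the steady-state reason for the gap has little force there.

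The alternative is to remove the 56 days from both sides and declare that attack-free status refers to the reduced period. For an end at Day 399 this leaves 394 − 56 = 338 days, or 86 + 253 = 339 if the two separate-period formulas are added. Use the same matching for any reduced-dose portion that starts before Day 147, should one occur; the documents do not show that one did.

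The cost is a sentence or two and a small programming check. Reported combined rates may become slightly less favourable.
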